4.3.1.2. GIS Responder

GIS responder at Week 12 is the secondary efficacy endpoint. It is defined as a subject who selected either 1) (significantly relieved) or 2) (moderately relieved) on the GIS questionnaire at Week 12. A subject with a missing response will be considered as non-responder in the specific visit. GIS responder will be derived at Day 1, Week 2, Week 4, Week 8, and Week 12 for all IBS subjects.

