10. Agrees not to participate in another clinical trial while participating in this study
11. **At Baseline (Visit 3),**
 - Must continue to meet all inclusion criteria
 - During any 5 days in the 7 days immediately prior to Baseline (Visit 3), as reported in the subject's daily pain diary:
 - Subject must have a weekly average of “worst abdominal pain in the past 24 hours” score of ≥ 3.0 on a 0- to 10-point NRS (see [Section 10.9](#) for NRS)

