8.2.2. Patient-reported Outcomes

Subjects will complete questionnaires at the site at the start of each required study visit (before vital signs and blood draws) to assess subject-perceived symptom relief and health-related quality of life. The PRO questionnaires are provided in Section □.

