10.7.3. Baseline, Visit 3 (Day 1)

- Assess inclusion/exclusion criteria
- Review concomitant medications
- Administer questionnaires (GIS, WPAI, IBS-QoL, and additional abdominal pain questions)
- Record blood pressure (average of 3 results; record each reading in the source document), body temperature, pulse, and weight
- Perform brief physical examination (heart, lungs, abdomen, external genitalia, perianal area, and any other areas as needed)
- Perform urine pregnancy test; if positive, perform serum test (subject may not begin double-blind treatment if serum pregnancy test is positive)
- Perform laboratory assessments, including urine dipstick
- Obtain subject randomization assignment
- Dispense double-blind study drug
- Administer witnessed dose of study drug
- Review AEs/SAEs

10.7.4. Double-blind Treatment Period Week 2 (\pm 4 days), Visit 4

- Administer questionnaires (GIS and additional abdominal pain questions)
- Review AEs/SAEs
- Review concomitant medications, including use of rescue medication from diary
- Record blood pressure (average of 3 results; record each reading in the source document), body temperature, and pulse
- Perform laboratory assessments, including urine dipstick
- Review remaining double-blind study drug from Baseline (Visit 3) for compliance and return to subject

10.7.5. Double-blind Treatment Period Week 4 (\pm 4 days), Visit 5

- Administer questionnaire (GIS and additional abdominal pain questions)
- Review AEs/SAEs
- Review concomitant medications, including use of rescue medication from diary
- Record blood pressure (average of 3 results; record each reading in the source document), body temperature, and pulse
- Perform laboratory assessments, including urine dipstick
- Dispense double-blind study drug

10.7.6. Double-blind Treatment Period Week 8 (\pm 4 days), Visit 6

- Administer questionnaires (GIS, WPAI, and IBS-QoL, and additional abdominal pain questions)
- Review AEs/SAEs
- Review concomitant medications, including use of rescue medication from diary
- Record blood pressure (average of 3 results; record each reading in the source document), body temperature, and pulse
- Perform laboratory assessments, including urine dipstick
- Dispense double-blind study drug

10.7.7. Double-blind Treatment Period Week 12 (\pm 4 days [Visit 7]), or Early Withdrawal

- Administer questionnaires (GIS, WPAI, IBS-QoL, and additional abdominal pain questions)
- Collect subject diary
- Review AEs/SAEs

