10.8. Appendix 8: Patient-Reported Outcomes Questionnaires

10.8.1. Global Improvement Scale

Global improvement assessment asks subjects to evaluate their current IBS status by asking the following question: How would you rate your IBS signs or symptoms overall over the past 7 days?

- 1) significantly relieved
- 2) moderately relieved
- 3) slightly relieved
- 4) unchanged
- 5) slightly worse
- 6) moderately worse
- 7) significantly worse

A responder is defined as a subject who answered that their symptoms were either moderately relieved or significantly relieved [Gordon, 2003; Lembo, 2001].

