6.2. Secondary Efficacy Analyses

[figure not shown]
The secondary efficacy endpoint GIS responder at Week 12 is defined in [Section 4.3.1](#). The proportion of responders will be analyzed similarly as described for primary endpoints using CMH for IBS-D and IBS_M subjects. When all subjects are included for the analysis, additional IBS subtype (IBS-D vs. IBSM will be used for stratification as well. The number and percentage of responder and non-responder for IBS-D, IBS-M and all IBS subjects will be tabulated by treatment and visit. GIS response data will be listed.

[figure not shown]
The secondary efficacy endpoints of proportion of IBS-D subjects who are API weekly responders with 40% improvement and API weekly responders with 50% improvement from Week 1 through Week 12 are defined in the [Section 4.3.1](#). The similar statistical analyses described in primary efficacy endpoint will be performed for these API weekly responders including subgroup analysis.

[figure not shown]
The secondary efficacy analyses will be primarily based on the FAS, unless stated otherwise.

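### The Week 12 GIS responder comparison does not use the Day 1 GIS answer, which can dilute the difference and let chance baseline imbalance into the estimate

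*SAP*

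**What the plan says.** The Week 12 GIS responder rate in all IBS subjects is a secondary endpoint (SAP 1.1.2; Protocol 3). SAP 4.3.1.2 defines the responder thus: "It is defined as a subject who selected either 1) (significantly relieved) or 2) (moderately relieved) on the GIS questionnaire at Week 12". Protocol 10.8.1 gives the same rule without reference to an earlier answer: "A responder is defined as a subject who answered that their symptoms were either moderately relieved or significantly relieved". The item is "How would you rate your IBS signs or symptoms overall over the past 7 days", and it names no time point against which relief is judged. A missing answer counts as non-response at that visit.

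The same item is given on Day 1 (Protocol 10.7.3: "Administer questionnaires (GIS, WPAI, IBS-QoL, and additional abdominal pain questions"). Protocol 8.2.2 places it early in the visit: "Subjects will complete questionnaires at the site at the start of each required study visit". The answer thus precedes double-blind drug but follows two weeks of single-blind placebo. No inclusion or exclusion criterion uses GIS. The symptom threshold at Baseline is a weekly pain average, a "score of ≥ 3.0 on a 0- to 10-point NRS" (Protocol 5.1).

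For the comparison, SAP 6.2 says "The proportion of responders will be analyzed similarly as described for primary endpoints using CMH". The strata are baseline pain (<6 vs ≥6) and, when all subjects are pooled, IBS subtype. Day 1 GIS is used descriptively: responder status is derived then as at later visits (SAP 4.3.1.2: "GIS responder will be derived at Day 1, Week 2, Week 4, Week 8, and Week 12 for all IBS subjects"), responders are tabulated by treatment and visit (SAP 6.2), and shift tables from baseline are listed as Tables 14.2.2.5 to 14.2.2.7 (SAP 11.1.1).

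**The concern.** A woman can satisfy the responder definition before randomized treatment starts, give the same answer 12 weeks later, and be counted as a response. Such women add responses to both arms that double-blind treatment did not produce. If the drug has less room to act in them, the difference between arms shrinks. Their numbers will also differ between arms by chance, and the planned strata do not correct for that.

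Other endpoints in the plan do look back to baseline. API response is a percentage fall from the baseline week (SAP 4.3.1.1). The mixed model for continuous endpoints includes the baseline score (Protocol 9.4.2.1). The two additional pain questions, asked at the same visits as GIS, are scored against Day 1, so that an unchanged answer is not an improvement (SAP 4.3.1.3). What is at stake is how precise and how readable a secondary estimate is, in a trial whose stated aim is estimation.

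**Working it through.** **The plan's own figure.** The only power figure is for the pain endpoint: 51% vs 31%, 45 per arm, two-sided α = 0.10, about 60% (Protocol 9.2).
- Pooled SE = √(2 × 0.41 × 0.59 / 45) = 0.1037.
- Unpooled SE = √((0.51 × 0.49 + 0.31 × 0.69) / 45) = 0.1015.
- Power = Φ((0.20 − 1.645 × 0.1037) / 0.1015) = Φ(0.29) = 61%.

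The figure reproduces, but it says nothing about GIS, for which the documents give no rates and no power.

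**Assumptions for GIS.** None of these comes from the documents except the planned 100 per arm.
- Share q of women who respond on Day 1: 10% to 30%, with lower values also considered.
- Of these, 70% to 85% still respond at Week 12, in either arm.
- Day 1 non-responders respond at 30% on placebo and 50% on vibegron.

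**Responses that predate the drug.** With no treatment effect, q × persistence gives 0.10 × 0.70 = 7 points up to 0.30 × 0.85 = 25.5 points of the Week 12 rate.

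**Dilution.** Overall difference = (1 − q) × 20 + q × e, where e is the effect in Day 1 responders.

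| q | e = 0 |
|---|---|
| 5% | 19 points |
| 10% | 18 points |
| 20% | 16 points |
| 30% | 14 points |

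The result depends on e. With e = 10 and q = 20%, the difference is 0.8 × 20 + 0.2 × 10 = 18 points.

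**Chance imbalance.** The SD of the between-arm difference in Day 1 response is √(2q(1 − q)/100): 4.2, 5.7 and 6.5 points at q = 10%, 20% and 30%. With no treatment effect, an imbalance moves the estimate by imbalance × (persistence − 0.30). One SD at q = 20% moves it by 5.7 × 0.40 = 2.3 to 5.7 × 0.55 = 3.1 points.

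**What a Day 1 stratum does.** Simulation used 20,000 trials per cell, 100 per arm, four equal pain-by-subtype cells, and the Mantel-Haenszel difference and variance of SAP 6.1.1. Ranges cover 70% to 85% persistence.

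| q | Power without stratum | Power with stratum |
|---|---|---|
| 10% | 83% | 86–87% |
| 20% | 74–75% | 79–81% |
| 30% | 64% | 69–73% |

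- Mean estimate at q = 20%: 16.0 points without the stratum, 16.2–16.3 with it. The dilution stays, because the stratified estimate still averages over Day 1 responders.
- SD of the estimate at q = 30% and 85% persistence: about 7.0 points without, about 6.4 with.
- Rejection rate with no effect, nominal 10%: about 10–11% without, about 11–12% with eight strata. Part of the power gain therefore comes from slightly small standard errors.
- At q = 5% or less the power gain is about 1 to 2 points (from a simpler run without the pain and subtype strata).

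**Day 1 non-responders only.** Under the same assumptions the difference in this group is the full 20 points, from about 90, 80 or 70 women per arm at q = 10%, 20% or 30%.

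**The case against.** The case for leaving the plan alone is substantial.

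- *Day 1 GIS is not ignored.* A reader might infer from the responder definition that the Day 1 answers go unused. They do not: responders are counted by treatment and visit, and the shift tables would show, by arm, women relieved at both times. SAP v2.0 added a GIS shift table (SAP 11.3). This stands. The gap is confined to the definition and the between-arm estimate.
- *There is no bias.* A reader might infer that the endpoint favours one arm. Randomization balances Day 1 status on average, and a difference over all randomized women is a legitimate target. This stands.
- *The size is assumed.* Every woman needs mean worst pain of at least 3.0 in the week before Day 1, close to the period GIS asks about, so few may report relief then. This stands; the share could be below 10%.
- *Relief is itself a change rating.* True, but the item gives no starting point, so a Day 1 answer may reflect the placebo run-in or earlier treatment. This stands in part.
- *A single Week 12 assessment.* A reader might add the lack of a repeat response as a fault. The documents do not show that one is needed, and the listed GIS tables cover all assessment weeks.
- *Stakes are low.* GIS is secondary, and all efficacy analyses are descriptive with nominal p-values. This stands.

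The exploratory analysis section (SAP 6.3) is redacted, so further use of Day 1 GIS there cannot be excluded.

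**Conclusion.** The point holds in a limited form. The Week 12 GIS definition and its CMH comparison make no use of a baseline answer that is already collected. Unchanged Day 1 responders count as Week 12 responders, and chance imbalance in Day 1 status is not adjusted for. If 10% to 30% of women respond on Day 1 and the effect is confined to the rest, a 20-point difference becomes 18 to 14 points. It shrinks less if Day 1 responders also benefit, and little if the share is 5% or less. Stratifying would add about 3 to 9 points of nominal power at shares of 10% to 30%.

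A reader might also infer that stratifying restores the 20 points. It does not; it narrows the spread around the diluted value. This is an improvement to consider, not an error that undermines the endpoint.

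**What to change.** In SAP 6.2, before unblinding:

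1. Add Day 1 GIS responder status (yes/no; missing = no) as a further stratum in the CMH risk difference for Week 12 GIS. This improves precision.
2. Add one supportive row giving the Week 12 GIS difference among women who were not GIS responders on Day 1. This addresses the dilution.

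The cost is a sentence or two of SAP text and one table row, with no new data. The downside is 2 × 2 × 2 = 8 strata for all IBS subjects. With equal cells of 25 per arm, a 10% share leaves an average of 2.5 Day 1 responders per arm in each pain-by-subtype cell, so the zero-count rule of SAP 6.1.1 would be needed more often. If this, or the no-effect rejection rate of about 11–12%, is a concern, keep the planned strata for the main result and present the version with the Day 1 stratum as supportive.

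In the same edit, correct the title of Table 14.2.2.7, which names IBS-M subjects although its analysis set is the FAS.

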4.3.1.3. Change from Baseline in API score

All endpoints will be derived at Baseline, Weeks 2, 4, 8 and 12.

- Weekly average of WAP score:
Derivation is defined as described in the first step in [Section 4.3.1.1](#).
- Weekly average number of pain-free days

[figure not shown]
Weekly average number of pain-free days is defined as the sum of all pain-free days in the past 7 days immediately prior to baseline visit (Day 1) or each of post-baseline Weeks (Weeks 2, 4, 8, 12), divided by the number of days with non-missing pain diary entries and then multiply 7. Weekly average will be set missing if more than 2 missed diary days over the past 7 days.

[figure not shown]
- Change from baseline in abdominal pain within 1 hour of eating

[figure not shown]
Change from baseline will be summarized categorically as “Improved (Yes to No)” vs “Not Improved”, where “Not Improved” is further categorized as “No Change”, “Worsened (No to Yes)”, or “Missing Post-baseline Assessment”.

- Change from baseline in abdominal pain associated with a bowel movement:

[figure not shown]
Change from baseline will be summarized categorically as “Improved (Yes to No)” vs “Not Improved”, where “Not Improved” is further categorized as “No Change”, “Worsened (No to Yes)”, or “Missing Post-baseline Assessment”.

[figure not shown]

4.3.2. Reporting Questionnaire Scoring

4.3.3. Study Day and Duration

Study day is relative to the start date of the double-blind treatment. This is used to describe the relative time of an event or assessment happened during the study. The first day of the study is defined as the day a subject first receives either vibegron or placebo in the double-blind treatment period. This is expected to be the same day as the randomization as Day 1. There is no study Day 0 is defined in the study.

- For an event or assessment that occurred on or after the first dose of double-blind treatment date:

:

Study day = Date of event or examination – date of first double-blind study treatment + 1

- For an event or assessment that occurred prior to the first dose of double-blind treatment date:

Study day = Date of event or examination – date of first double-blind study treatment

Similarly, a duration between any two dates (such as AE duration) expressed in days will be calculated using the following conventions:

- Duration = Later date – earlier date + 1, if the earlier date is on or after the date of first dose of double-blind treatment
- Duration = Later date – earlier date, if the earlier date is prior to the date of first dose of double-blind treatment

4.3.4. Baseline and Change from Baseline

In general, the last recorded value on or prior to the date of double-blind treatment start will serve as the baseline measurement for efficacy endpoints while the last recorded value prior to first dose of double-blind treatment will serve as the baseline measurement for safety endpoints. The mean of the multiple values will be used as baseline for the following situations:

- If multiple measurements are scheduled on the same baseline day (i.e., blood pressure)
- If multiple measurements are collected on the same baseline day without the time or “repeat” status to differentiate the records

Change from baseline will be calculated as the post-baseline value minus the baseline value. Percentage change from baseline will be calculated as the change from baseline divided by the baseline value, multiplied by 100. If either the baseline or post-baseline value is missing, then change from baseline and percentage change from baseline will be set to missing.

5. DEMOGRAPHIC, OTHER BASELINE CHARACTERISTICS AND MEDICATION

5.1. Subject Disposition and Withdrawals

Subject disposition will be summarized by treatment group for the Screened, Run-in and Randomized Sets separately. The summary table will present the frequency and percentage of subjects in each of the analysis sets and those who discontinued the study prematurely along with the primary reasons for discontinuation.

For the summary under the Randomized Set, the following additional categories will be presented as well; randomized, received treatment with study drug, did not receive treatment with study drug, completed treatment with study drug, discontinued treatment with study drug (and reason), and withdrawn from study (and reason).

The frequency and percentage of subjects with at least one major Protocol Deviation (PD), major PD by classification and reasons/category for PD will be summarized by treatment arm and by FAS-D, FAS-M and FAS. Inclusion in each of the analysis sets (SAF, FAS, FAS-D, etc.), and any reasons for exclusion will be summarized by treatment arm for the Randomized Set.

Screen Failure, Run-in and Double-Blind Period disposition, with reasons for discontinuation of study will also be listed, including the date of discontinuation and date of last contact. The date of last contact is the maximum date of study discontinuation, follow-up or the return of study medication. When lost to follow-up, the latest date of assessment/event in the database will be used as the last known date of the subject in study.

Eligibility criteria, screening and run-in failures (including date and primary reason for failure), and informed consent (protocol version, informed consent version date and date signed) will be listed for all subjects screened.

A summary of randomized subjects by country, investigator name and site identification will be provided.

Randomization details will also be listed, including the date of randomization, randomization number and randomization strata. A listing will also be provided for the subjects who had misclassification of the stratification factors (i.e., randomization stratification does not match actual stratification values). The actual stratification is based on medical history lower level terms of "Irritable bowel syndrome" which indicates the subjects has a history of IBS-M and the term of "Diarrhea predominant irritable bowel syndrome" which indicates the subject has a history of IBS-D. If more than one term is available, the term ongoing just prior to randomization should be used. In the rare event that no medical history term is able to be mapped to either IBS-D or IBS-M then the actual stratification will be assigned the value of the randomization strata.

5.2. Demographic and Baseline Characteristics

All demographic and baseline characteristic data will be summarized by treatment group using descriptive statistics for all IBS subjects, IBS-D and IBS-M based on the FAS. In addition, the summary will be prepared for PPS-D.

The summary table will include age, age category ((<40 , ≥ 40 to <65 , ≥ 65 years), sex, child bearing potential (Yes/No), ethnicity, race, baseline abdominal pain intensity score (<6 vs ≥ 6), baseline IBS subtype (IBS-D vs. IBS-M) (only for all IBS subjects), previous IBS diet (Yes/No), category of previous IBS diet if Yes, baseline hypertension category (Hypertension vs. normotensive), pre-existing hypertension (Yes/No), weight, height and BMI.

Baseline Hypertension will be defined as baseline systolic blood pressure (SBP) ≥ 140 mmHg or baseline diastolic blood pressure (DBP) ≥ 90 mmHg, regardless of medical history.

Pre-existing hypertension will be defined as having a medical history of hypertension or baseline hypertension (baseline SBP ≥ 140 mmHg or baseline DBP ≥ 90 mmHg). The following list of preferred terms will be used to search for medical history of hypertension:

- Accelerated hypertension
- Diastolic hypertension
- Essential hypertension
- Hypertension
- Hypertensive crisis
- Hypertensive emergency
- Hypertensive heart disease
- Malignant hypertension
- Malignant hypertensive heart disease

- Secondary hypertension
- Supine hypertension
- Systolic hypertension

Age (years), height (cm), weight (kg), and BMI captured at Screening will be summarized as a continuous variable.

All demographic data will be listed.

5.3. Other Baseline Characteristics

The data from the Daily Evening Pain Diary and Bowel Movement diary during run-in period (reviewed at Visit 3 Baseline visit) prior to first double-blind dose will be used as baseline for each subject. This includes endpoints:

- Weekly average of worst daily pain score,
- Weekly average number of pain-free days
- Daily average bowel urgency episodes,
- Weekly average number of days with bowel urgency,
- Abdominal pain within 1 hour of eating (Yes vs No),
- Abdominal pain associated with a bowel movement, (Yes vs No)
- Weekly average number of days with recurrent bowel movement,
- Daily average number of bowel movements,
- Weekly average number of days with diarrhea (Bristol Type 6 or 7),
- Weekly number of days with diarrhea (Bristol Type 6 or 7)
- Weekly average number of days with at least 1 stool with Bristol Type 3, 4, or 5 consistency
- Weekly average number of stools with Bristol Type 3, 4, or 5 consistency

In addition, the following parameters will be presented in the baseline table

- Daily average stool consistency
- Daily average number of diarrhea bowel movement
- Daily average number of stools with Bristol Type 3, 4, 5 consistency
- Weekly average number of days with constipation (Bristol Type 1 or 2)
- Daily average number of stools with constipation (Bristol Type 1 or 2)
- Weekly average number of stools with constipation (Bristol Type 1 or 2)

These will be summarized by IBS subtype (IBS-D, IBS-M) and for all IBS subjects, and treatment group using descriptive statistics for continuous data for all subjects in each analysis set.

5.4. Medical History and Concomitant Disease

Descriptions of medical history findings will be coded using Medical Dictionary for Regulatory Activities (MedDRA) version 23.0 or higher.

A disease or illness reported as medical history without a start date will be included in medical history without a date assigned. Medical history will be sorted by descending overall frequency, by system organ class (SOC) and preferred term (PT) in the summary table. Medical history data listings will be sorted by treatment, subject number, start date, SOC and PT.

